#### 1. Sexual outcomes

- a. The presence of severe erectile dysfunction, with or without the use of phosphodiesterase-5 inhibitors, at 12 and 36 months, as measured by the erectile function domain of the IIEF-15 questionnaire in those with absence of severe erectile dysfunction at baseline
- b. The presence of any new/ progression of erectile dysfunction at 12 and 36 months, measured as an at least 6 point drop in IIEF-15 questionnaire score within the erectile function domain.
- c. Time to return of erectile function (absence of severe ED on IIEF-15 questionnaire)
- d. Need for phosphodiesterase-5 inhibitors to maintain erectile function sufficient for penetration at 36 months
- e. The presence of ejaculatory function at 12 and 36 months as measured by the orgasmic function domain of the IIEF-15 questionnaire

- f. The presence of orgasmic function at 12 and 36 months as measured by the orgasmic function domain of the IIEF-15 questionnaire
- g. Presence of pain during intercourse requiring premature cessation of intercourse i.e. prior to climax, at 36 months

2. Urinary incontinence

- a. Presence of urinary incontinence (any pad usage plus any leakage of urine) as determined by the UCLA-EPIC urinary continence questionnaire, at 12 months and 36 months, in those men with no urinary incontinence at baseline
- b. Presence of urinary incontinence (requiring any pad usage) as determined by the UCLA-EPIC urinary continence questionnaire at 12 months and 36 months
- c. Time to return of urinary continence (as determined by UCLA-EPIC Urinary domain questionnaire)

3. Other functional outcomes

- a. Grading of lower urinary tract symptoms as determined by IPSS scores at 12 months and 36 months
- b. Presence of bowel toxicity as determined by the UCLA-EPIC Bowel questionnaire at 12 months and 36 months
- c. Anxiety levels as measured by the Memorial Anxiety Scale for Prostate Cancer
- d. General and prostate health related QoL as measured using EQ-5D-5L and FACT-P Version 4

Patients will also be asked to complete Health Economics questionnaires (in the form of self-reported diaries) in which we will ask them to identify and record items relating to utilisation of the health care resources mentioned and any other relevant health care resources. The self reported diaries will be piloted and adapted during Stage 1 of the PART study. Stage 1Stage 1Stage 1Stage 1Stage 2

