The EQ-5D-5L will be used to measure patient health-related QoL at baseline, 6 weeks and every 3 months for the first year and every 6 months thereafter. Patient's 5-dimension (mobility, self-care, usual activities, pain/discomfort, anxiety and depression) EQ-5D-5L health state classification at each trial time point will be converted into a utility score on a 0 to 1 scale where 0 is equivalent to dead, and 1, to perfect health. This conversion will be made using the new algorithm based on the UK value set currently being conducted by the Euroqol Group, (if available at the time of analysis). If not available, the current crosswalk algorithm provided by the EuroQol group and algorithm estimated by Dolan *et al.* (derived from a survey of the UK population (n=3337)) will be used. Utility values in the tariff set range from no problems on any of the five dimensions in the EQ-5D descriptive system (value=1.0) to severe or extreme problems across all five dimensions (value=-0.594) (Dolan, Gudex et al. 1996, Dolan 1997). The utility scores will be combined with within-trial survival data to estimate the QALY's required for the cost-utility analysis.

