#### 7.4. Baseline Assessments (at screening visit)

- Review of medical history and Physical Examination, including digital rectal examination and routine blood tests
- Completion of validated patient questionnaires (refer to Appendix B)
- PSA blood test

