**Stage 2:**

If Stage 1 is successful, we will apply to the HTA for additional funding with the aim of recruiting a further 600-800 additional patients over 5 years (Stage 2) in participating centres (minimum 10) with appropriate skill mix. We will review the statistical power calculations in the light of information from the first 100 patients – in particular, the true incidence of unilateral disease qualifying for PA, the comparative quality of life scores, and primary treatment failure rates. A pragmatic decision will then be made on the final recruitment target. We anticipate that QoL will be better with ablative therapy than radical surgery, particularly functional outcomes such as urinary continence and erectile function, such that an increase of 10% in the primary treatment failure rate (i.e. 25% increased to 35%) might well be considered acceptable to underpin a change in clinical practice. Even allowing for a 10% drop-out rate, 800 randomised 1:1 between PA and RP would provide 80% power at  $2p < 0.05$  to detect a 10% worse treatment failure rate with ablative therapy than radical surgery. If primary treatment failure rates were substantially more than 10% higher with PA than RP then this would be detected with high statistical power enabling a good point estimate of the difference and meaningful subgroup investigations to identify any patient or tumour characteristics that were predictive of treatment failure.

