**10.3. Analysis of Outcome Measures**

Time to primary treatment failure will be analysed by standard logrank methods. Dichotomous variables (such as presence absence of erectile dysfunction) and ordinal variables (such as toxicity grades) will be analysed using Mantel-Haenszel tests. Continuous outcome measures such as quality of life scores will be analysed using independent t-tests or repeated measures regression techniques.

Analysis of healthcare resource use, cost and EQ-5D data - Stage 1

The purpose of the economic analysis in Stage 1 of the PART study is to evaluate the response rate and completion rates of the resource use questionnaires and EQ-5D-5L instrument and to assess the feasibility and usefulness of the self-reported patient resource use diary compared with electronic patient-data capture. A preliminary analysis of the resource-use data and cost-consequence analysis will be used to update the sample size calculations required for Stage 2 of the PART study.

Analysis of healthcare resource use, cost and EQ-5D data - Stage 2*Missing data:*

The resource-use/cost and EQ-5D data will be investigated to ascertain the extent of missing data and whether this is due to random missingness and/or censoring. If this amounts to more than 10% of the data collected missing at random, multiple imputation using standard methods will be undertaken (Rubin and Schenker 1991, Briggs, Clark et al. 2003). The focus of studying the healthcare resource use is to investigate how partially ablative therapies in prostate cancer patients affect the health care costs. With the aim of the economic analysis to estimate how the costs of the intervention minus the difference in health care costs between the intervention and standard treatment (radical prostatectomy) group of patients balances against the health care benefits. An in depth analysis of the healthcare resource use and their costs will be conducted. First the impact of the partially ablative therapies on prostate-cancer specific healthcare resource use/costs (including side-effects, recurrence and progression related costs) will be evaluated over the duration of the study and compared with those arising from radical surgery. Secondly, a regression

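### Section 10.3 permits unadjusted t-tests on continuous quality-of-life scores and does not commit to using the baseline scores already collected

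*Protocol*

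**What the plan says.** For continuous outcomes, Section 10.3 states: "Continuous outcome measures such as quality of life scores will be analysed using independent t-tests or repeated measures regression techniques". It does not say which method applies to which score or visit. It neither requires nor excludes a baseline covariate.

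Baseline data will exist. Appendix B marks IIEF-15, IPSS, UCLA-EPIC, EQ-5D-5L, FACT-P and the modified Memorial Anxiety Scale at visit 2, before the procedure, and again at nine follow-up visits from 6 weeks to 36 months. Section 7.4 lists the questionnaires among the baseline assessments. Section 5.3 confirms this for one instrument: "The EQ-5D-5L will be used to measure patient health-related QoL at baseline, 6 weeks and every 3 months for the first year".

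Other types of outcome are handled separately in Section 10.3: "Dichotomous variables (such as presence absence of erectile dysfunction) and ordinal variables (such as toxicity grades) will be analysed using Mantel-Haenszel tests". Two of the functional endpoints in Section 5.1 are restricted by baseline status: severe erectile dysfunction is assessed "in those with absence of severe erectile dysfunction at baseline", and one incontinence endpoint "in those men with no urinary incontinence at baseline".

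Section 10.1 (Stage 2) explains why these outcomes matter: "We anticipate that QoL will be better with ablative therapy than radical surgery, particularly functional outcomes such as urinary continence and erectile function". That expectation is the reason given for tolerating a higher failure rate with ablation.

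**The concern.** An independent t-test on follow-up scores makes no use of the baseline. Variation between men that was already present before treatment stays in the standard error, and any chance imbalance at baseline stays in the estimate. A test at a single visit also drops every man without that visit's form, even if he returned forms at the visits on either side. A repeated-measures model with the baseline score avoids both losses and needs no further data.

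A comparison of ablation with surgery turns on whether function and quality of life gain enough to offset more treatment failures, so precision on the scores is worth having. It is scarcest in Stage 1. Section 10.1 intends to use comparative quality-of-life scores from the first 100 men when reviewing the power calculation for Stage 2.

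**Working it through.** **Inputs from the protocol.** Section 10.1 (Stage 2): 800 men, 1:1, 80% power, two-sided 5% level, 10% drop-out, failure 25% against 35%. The protocol gives no standard deviation, effect size or power for any quality-of-life score.

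**Assumptions.** The correlation r between baseline and follow-up score is not given, so 0.3, 0.5 and 0.7 are used to show a range. Differences are in units of the follow-up SD. The 10% drop-out is applied to the scores as well.

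**Step 1: the plan's own figure.** Section 10.1 says "800 randomised 1:1 between PA and RP would provide 80% power at" a two-sided 5% level. With p = 0.25 and 0.35 and mean 0.30:

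n per arm = [1.960 × √(2 × 0.30 × 0.70) + 0.842 × √(0.25 × 0.75 + 0.35 × 0.65)]² / 0.10² ≈ 329

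That is 658 in total, or 732 after dividing by 0.9. With continuity correction it is 349 per arm, 698 in total and 776 after drop-out. At 720 evaluable men the uncorrected power is 83.5%. So 800 is adequate for the failure rate. This figure is used below only for its number of evaluable men: 800 × 0.9 = 720, or 360 per arm.

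**Step 2: variance of the two analyses.** With SD = 1 and n men per arm:

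- t-test on follow-up scores: variance = 2/n
- baseline-adjusted analysis: variance = (2/n)(1 − r²)
- ratio, t-test to adjusted: 1/(1 − r²)

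**Step 3: numbers at 360 per arm.** The difference detectable by the t-test with 80% power is (1.960 + 0.842) × √(2/360) = 0.209 SD. The adjusted analysis multiplies this by √(1 − r²).

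| r (assumed) | 1 − r² | Variance ratio | SE excess of t-test | Detectable difference, adjusted | Adjusted power at 0.209 SD | Men a t-test needs to match 720 adjusted |
|---|---|---|---|---|---|---|
| 0.3 | 0.91 | 1.10 | 4.8% | 0.199 SD | 83.6% | 791 |
| 0.5 | 0.75 | 1.33 | 15.5% | 0.181 SD | 89.9% | 960 |
| 0.7 | 0.51 | 1.96 | 40.0% | 0.149 SD | 97.5% | 1,412 |

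**Step 4: Stage 1 alone.** With 100 men less 10% (45 per arm), the t-test detects 0.591 SD. The adjusted analysis detects 0.563, 0.511 or 0.422 SD.

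**Step 5: a t-test on change scores.** This reading would use the baseline. With equal SDs at both times its variance is (2/n) × 2(1 − r), that is 1.4, 1.0 or 0.6 times the follow-up-score variance. The adjusted analysis has 0.91, 0.75 or 0.51 times. A change-score t-test is therefore still less precise, by a factor 2/(1 + r) = 1.54, 1.33 or 1.18.

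**The case against.** Three objections carry weight.

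1. **The t-test is only one of two options.** A reader might infer that unadjusted t-tests are the planned or default analysis. The text does not say that: repeated-measures regression stands beside the t-test with equal rank and can take the baseline score as a covariate or as the first response. The absence of baseline adjustment is silence, not a stated choice. If the regression is used with the baseline score, the loss may be nil.

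2. **Covariates are usually settled in the analysis plan, which is not shown.** This is right as far as omitted detail goes. But the protocol does more than omit detail: it names a weaker method as acceptable, and an analysis plan that adopted it would comply fully.

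3. **The endpoints said to favour ablation are mostly not analysed by t-test.** A reader might infer that the functional case for ablation rests on t-tests. Section 5.1 defines the continence and erectile endpoints mainly as presence or absence, or as time to return. The dichotomous ones go to Mantel-Haenszel tests, and some already condition on baseline status or on a drop in score. This stands, and it limits the point to IPSS, FACT-P, EQ-5D-5L, the anxiety scale, and IIEF or EPIC domain scores where these are analysed as scores.

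The complaint about missing forms is also partly met for EQ-5D. Section 10.3 plans multiple imputation above a 10% threshold and a regression framework across time points. Both belong to the economic analysis and do not cover the other instruments.

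**Conclusion.** The point holds in a limited form. Section 10.3 leaves open a method that ignores baseline scores the trial will hold for every instrument, and it does not commit to the better one. If the t-test is used on follow-up scores, variance is inflated by 1.10, 1.33 or 1.96 for r = 0.3, 0.5 or 0.7, and men without that visit's form are lost from that comparison. The size rests on an assumed r. The conversion into numbers of men also rests on 720 evaluable men, in a Stage 2 that is not yet funded and whose size is to be reviewed.

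It would go too far to call the t-test biased. Under randomisation with complete data it is unbiased, and a chance baseline imbalance adds noise, not systematic error. The outcomes affected are secondary, and the primary failure comparison and its sample size are untouched. Severity is minor: a free improvement.

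**What to change.** In Section 10.3, delete the t-test option and replace the sentence on continuous outcomes with wording such as:

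> Continuous scores will be analysed with a mixed model for repeated measures over all scheduled follow-up visits. Terms are treatment, visit, treatment by visit, baseline score and baseline score by visit. Adjusted treatment differences at 12 and 36 months will be reported with 95% confidence intervals.

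The rules for dichotomous and ordinal outcomes need no change on this account. The model uses all returned follow-up forms and relies on data being missing at random given the scores included, which the analysis plan can state.

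The cost is a few lines of text. No visit, form or patient is added, because Appendix B already collects what the model needs.

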#### *Within-trial cost-effectiveness analysis:*

The economic evaluation will compare the implementation of partially ablative therapy with standard radical surgery for prostate cancer patients. We plan to conduct a within-trial economic analysis, then if the trial demonstrates clinical effectiveness, these within trial results will be used to extrapolate beyond the trial endpoint and model the likely life-time cost-effectiveness. A within-trial cost-consequence analysis will initially be reported, describing all the important results relating to the health care resource use, costs and consequences (side-effects, disease progression, recurrences) of partially ablative therapy compared with radical prostatectomy for prostate cancer patients. Subsequently, a within-trial cost-utility analysis will determine cost per quality-adjusted life year (QALY) gained. The use of QALY's aims to capture the impact of disease progression and non-fatal events on health-related quality of life in addition to any impact on survival. This is particularly pertinent to this trial where we are trying to evaluate the trade-off between an improved quality of life due to reduced side-effects with the increased possibility of recurrence. Discounting at a rate of 3.5% will be applied. Results will be expressed in terms of incremental cost-effectiveness ratios (ICERs). Sensitivity analysis will test the robustness of the results. This will explore uncertainties in the trial based data itself, the methods employed to analyse the data and the generalisability of the results to other settings, to determine the impact of changes on results. Non-parametric bootstrapping and probabilistic sensitivity analysis will explore uncertainty in the confidence placed on the results of the economic analysis and cost effectiveness acceptability curves will be presented.

#### *Lifetime cost-effectiveness analysis:*

If trial results demonstrate clinical effectiveness, extrapolation beyond the trial period of 78 months will be undertaken. The methods used will depend on the within trial data, but will either use parametric methods as set out by the NICE Decision Support Unit (Latimer 2011) or use a lifetime decision-model, in order to determine the long-term cost-effectiveness of the intervention in terms of cost per QALY gained. This will be based on the individual patient data (using the results from the regression analysis outlined above) from the study and external data (where required). It will be carried out from an NHS and Personal Social Services perspective, to take into account health care costs and longer term social care costs and the impact on life expectancy, quality adjusted life expectancy. The model will be run over remaining patient lifetime, with costs and benefits discounted at a rate of 3.5%. The lifetime cost-effectiveness analysis will be driven by the decision analytic model and the way treatment effects are propagated in the model. Extensive deterministic sensitivity analysis will be undertaken to assess the impact of changing the values of key parameters and will be used to explore the importance of modelling assumptions. Probabilistic sensitivity analyses will be conducted to deal with uncertainty in model parameters and cost-acceptability curves presented.

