##### STAGE 2:

Objectives	Outcome Measures

Primary Objective
 
 
- To compare treatment failure rates between the two treatment groups.
 
	
 
- Primary treatment failure as demonstrated by the need for whole gland ablation and/or secondary interventions.
 

Secondary Objectives
 
 
- To compare the short, medium and long-term effects of both treatment arms
 
- The effect on Quality of Life and Health Resource Utilisation of both treatment arms
 
- The role of imaging by mpMRI and biopsy protocols in determining suitability of patients for focal therapy
 
	
 
- Short, medium and long-term adverse events related to treatments
 
- Disease progression including development of metastases
 
- Disease-specific and all-cause mortality
 
- Quality of life using conventional questionnaires (IIEF-15, IPSS, EQ-5D-5L, FACT-P, UCLA-EPIC)
 
- The role of imaging by mpMRI and biopsy protocols in determining the suitability of patients for focal therapy using data collected in the CRF.
 

--	--

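### The lifetime cost-effectiveness model depends on an undefined showing of clinical effectiveness, a condition that, read on the primary outcome, conflicts with the trade-off the economic evaluation is meant to weigh

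*Protocol*

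**What the plan says.** Section 10.3 states the condition twice. Under the lifetime analysis: "If trial results demonstrate clinical effectiveness, extrapolation beyond the trial period of 78 months will be undertaken". Under the within-trial analysis: "then if the trial demonstrates clinical effectiveness, these within trial results will be used to extrapolate beyond the trial endpoint". Neither place says what would count as clinical effectiveness, on which outcome, or by what test.

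Three other statements bear on how the condition can be read.

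- The Stage 2 primary objective in Section 4 is "To compare treatment failure rates between the two treatment groups".
- Section 10.1 says of quality of life: "We anticipate that QoL will be better with ablative therapy than radical surgery". It concludes that "an increase of 10% in the primary treatment failure rate (i.e. 25% increased to 35%) might well be considered acceptable", and states power "to detect a 10% worse treatment failure rate with ablative therapy than radical surgery".
- Section 10.3 says the economic evaluation is there to "evaluate the trade-off between an improved quality of life due to reduced side-effects with the increased possibility of recurrence".

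The within-trial cost-consequence and cost-utility analyses carry no condition. Nor do the regressions of cost and EQ-5D data in Section 10.3, which are described as feeding the extrapolation model.

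**The concern.** The design allows for PA to do worse on the primary outcome and better on quality of life. Whether that exchange is worthwhile depends on what follows a treatment failure, and much of that may come late. Section 3.4 names progression to metastases as a key caveat of the focal strategy, and Section 6.2 requires a life expectancy of at least 10 years. Scheduled visits and EQ-5D forms end at 36 months (Section 7.6, Appendix B).

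The lifetime model is the planned analysis that carries costs and QALYs beyond that point. If it runs only after a favourable primary result, it is absent when failures are more frequent with PA, which is when their later consequences most need valuing. Decision makers would then have only the within-trial ratio.

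**Working it through.** **Inputs (Section 10.1, Stage 2).** 800 men, 1:1, 10% drop-out, two-sided 5% level, failure 25% with radical prostatectomy (RP) and 35% with PA. Evaluable per arm: 800 × 0.90 / 2 = 360.

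**Reproducing the stated 80% power.**

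- Required per arm: [1.96·√(2×0.30×0.70) + 0.842·√(0.25×0.75 + 0.35×0.65)]² / 0.10² = 329, so 658 / 0.90 = 732 in total. With continuity correction, 349 per arm, so 698 / 0.90 = 776 in total.
- Power at 360 per arm: SE under the null = √(2×0.30×0.70/360) = 0.0342; SE under the alternative = √[(0.1875 + 0.2275)/360] = 0.0340. Power = Φ[(0.10 − 1.96×0.0342)/0.0340] = 83.5%.
- The primary analysis is a logrank test. The matching hazard ratio is ln 0.65 / ln 0.75 = 1.50. That needs 193 events; 360 × (0.25 + 0.35) = 216 are expected, giving 84%.

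The stated 80% is sound and slightly conservative, so the two-proportion approximation is adequate for what follows.

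**How often the condition would be met.** Keep RP at 25% and let d be the true excess failure with PA.

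- *Superiority reading* (PA significantly better on failure): Φ[(−d − 1.96·SE₀)/SE₁], where SE₀ is the pooled and SE₁ the unpooled standard error.
- *Non-inferiority reading* with a 10-point margin: Φ[(0.10 − d)/SE₁ − 1.96]. The margin is my assumption, taken from the excess the protocol calls possibly acceptable. The protocol sets none.

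| True excess d | PA superior | PA non-inferior, 10-point margin |
|---|---|---|
| 0 | 2.5% | 87% |
| 2 points | 0.5% | 69% |
| 5 points | 0.03% | 32% |
| 10 points | below 0.0001% | 2.5% |

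For example, at d = 0.05, SE₁ = √[(0.1875 + 0.21)/360] = 0.0332 and Φ(0.05/0.0332 − 1.96) = 32%. At d = 0.10 the second formula reduces to Φ(−1.96) = 2.5%. On both readings the chance falls as PA does worse.

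**Horizon.** The 78 months in the lifetime paragraph equals the two planned stages in the Synopsis, 18 + 60 months. That is calendar time for the programme. The visit schedule gives each man 36 months.

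**The case against.** The strongest reply is that the term is undefined, not defined as superiority. Section 10.1 says a 10-point excess might support a change in practice because quality of life is expected to be better. A trial judged effective on that exchange would meet the condition and the model would run. This stands: the 2.5% at equal failure rates belongs to one reading only. Section 10.1 also calls the 10-point excess acceptable; it does not forecast it.

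A reader might go further and infer that the cost-effectiveness result is bound to be tilted towards ablation. The documents do not show that. The within-trial analyses are unconditional, report disease progression and recurrences, and cost the treatment of recurrence (Section 5.3), so failures during follow-up do count against PA. A tilt from the missing later years is plausible, but nothing in the protocol lets its size be computed. The HIFU survival figures in Section 3.3 come from uncontrolled series that include salvage treatment, so they do not settle it. Section 13.5 also foresees long-term follow-up through NHS records, which may add deaths after 36 months, though no EQ-5D form is scheduled beyond that visit.

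A reader might also infer that the missing-data rule in Section 10.3, "If this amounts to more than 10% of the data collected missing at random, multiple imputation using standard methods will be undertaken", switches imputation off in the situation the trial expects and leaves a complete-case analysis. That is not supported. The protocol forecasts no questionnaire missingness, does not say that incomplete cases are dropped at or below 10%, and gives no denominator for the 10%. Such detail can properly sit in an analysis plan.

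Finally, this is a secondary analysis in a stage not yet funded, whose size is to be reviewed after Stage 1. That limits the weight of the point, not its correctness.

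**Conclusion.** The point holds for the lifetime model. An undefined condition governs whether it is run, and read on the primary outcome that condition conflicts with the design in Section 10.1 and the stated purpose in Section 10.3. At a true 10-point excess the chance of meeting it is 2.5% or less under either reading tested. At equal failure rates it ranges from 2.5% to about 87% on the definition alone, which shows how much the missing definition matters. These figures assume 360 evaluable men per arm, 25% failure with RP and, for non-inferiority, a 10-point margin that the protocol does not set. A reading that credits better quality of life would let the model run, but the text does not state one.

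What is at risk is the lifetime analysis only. The within-trial cost-utility analysis, the primary comparison, the sample size and the error rate are unaffected. The change should be made before Stage 2.

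**What to change.** Delete the condition in both paragraphs of Section 10.3 and state that the lifetime model will be run whatever the result on treatment failure. Defining the term instead would remove the ambiguity but would still make the analysis depend on the result.

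The cost is two sentences, and modelling work that was conditional becomes certain. The regressions that feed the model are already planned without condition.

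Minor note for the analysis plan: state whether the 10% in the missing-data rule counts items, forms or men, and name the method used at or below it. Do not make missing at random part of the trigger, because it cannot be verified from the observed data.
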